## 7. MEASUREMENTS AND STUDY EVALUATIONS

**Serum vitamin C level.** We will measure participant's serum vitamin C level at baseline and Month 3 to measure the effect of vitamin C supplementation. Sample vitamin C will be measured in serum using MyBioSource ELISA kits.

**Symptom burden.** Physical symptom burden will be measured using items from the Memorial Symptom Assessment Scale—Heart Failure (MSAS-HF). The MSAS-HF is an 8-item questionnaire adapted from Portney's Memorial Symptom Assessment Scale that is designed to provide multidimensional information about HF symptoms experienced by patients with HF. Patients will be first asked if the symptom was present during the previous 7 days. If present, three characteristics of each symptom will be rated: frequency of symptom, severity of symptom, and degree of symptom distress. Frequency is rated on a scale from 1 to 4 (rarely to almost constantly), severity rated on a scale from 1 to 4 (mild to very severe) and distress rated on a scale from 0 to 4 (not at all to very severe). Burden score for each symptom can range from 0 (no burden) to 12 (greatest symptom frequency, severity, and distress). The scale has good reliability, ranges of 0.73-0.92 in patients with HF.

**Health-related quality of life (HRQOL).** The Minnesota Living with Heart Failure questionnaire (MLHFQ) is a measure of HRQOL that assesses the patient's perceptions of the

influence of HF on physical and emotional aspects of life. The 21 items are summed with higher scores indicating worse HRQOL. The questionnaire has been widely used to measure quality of life in this population. Researchers have demonstrated evidence for validity and reliability (Cronbach's alphas ranging from .88 to .93). The MLHFQ was used in our study that demonstrated a significant relationship between vitamin C deficiency and HRQOL, as well as between HRQOL and re-hospitalization or mortality.

**Cardiac function.** Impedance Cardiography is a measurement method that is primarily used to determine aspects of Cardiac Output (CO) that we will use the MindWare Mobile impedance cardiograph (model number 50-2303-00) in this study. CO is the total amount of blood, pumped from both the left and right ventricles of the heart for each of its successive systolic phases, over the course of one minute. Left ventricular cardiac output is the CO from the left ventricle only and can be estimated via a non-invasive technique called Impedance Cardiography (ICG), which provides an approximation of Stroke Volume (SV) ( $CO=SV*HR$ ). We will measure patient's cardiac output and heart rate variability to reflect the participant's cardiac function using impedance cardiograph that is non-invasive, reproducible, valid and widely used in patients with cardiovascular disease. The MindWare Mobile impedance cardiograph is a commercially available impedance cardiograph that has been widely used in research studies. The MindWare Mobile impedance cardiograph is a small, portable device with a high precision frequency constant current of 400 micro amps which allows measurement of the impedance changes across the thorax to monitor cardiac function.

**Oxidative stress biomarker.** We will measure 8-iso-PGF2a isoprostane as a biomarker of oxidative stress. Elevated level of 8-iso-PGF2a isoprostane will serve as a biomarker of increased lipid peroxidation due to oxygen free radical production exceeding antioxidant capacity and will be measured in our Biobehavioral Lab. The level of the biomarker is expected to decrease in response to the vitamin C supplementation. Venous blood will be drawn into vacutainers containing trisodium citrate, EDTA and/or BHT depending on the analysis, centrifuged in a refrigerated centrifuge and serum separated and allotted to micro-tubes and kept at -70°C prior to analysis. 8-iso-PGF2a isoprostane will be measured in serum using Cell Biolabs ELISA kits. For all assays, samples and standards will be run in duplicate and inter- and intra-assay determined to assure accuracy and reproducibility.

**Covariates.** We will collect participants' demographic and clinical data to assess sample characteristics, characterize the sample, and obtain data on potential confounding variables.

## **8. SAFETY EVALUATIONS**

All participants will receive a phone call within 1 week after enrollment, and also at Month 1 and Month 2 to follow-up whether they are taking the investigational pills (vitamin C or placebo) daily and whether they have any adverse events from taking the investigational pills (see checklist in Appendix). If any adverse events were found/reported, we will follow them per recommendations of the medical monitor until the event resolves. [name], a nurse practitioner with specialty in heart failure management at UNC Meadowmont Cardiology clinic will serve as a medical monitor on this study. Any adverse event will be reported to [name] in 72 hours or less. [name] will determine the severity of the adverse events and advise whether the participant needs to stop taking the investigational pills, withdraw from the study, or any medical treatment is needed. We will follow [name]' advice immediately.

When subjects have AE (define as new signs and symptoms after taking investigational drugs, such as digestive distress--diarrhea, nausea, abdominal bloating and any other unanticipated adverse events that could possibly be related to the intervention). We will report to

[name] to determine the severity of the AEs (see below). When mild AE is determined, subjects will continue to take their investigational drugs without further treatment and the RA will keep following up subject's AE until AE resolves. When moderate AE is determined, we will ask subjects to stop taking their investigational drug, advise them to seek medical treatment, and continue to follow up until the AE resolves. If severity of any AE is more than moderate, we will ask subjects to seek for emergent medical treatment.

- Mild Adverse Event – Event results in mild or transient discomfort, not requiring intervention or treatment; does not limit or interfere with daily activities (e.g., insomnia, mild headache).
- Moderate Adverse Event – Event is sufficiently discomforting so as to limit or interfere with daily activities; may require interventional treatment (e.g., fever requiring antipyretic medication).
- Severe and undesirable Adverse Event – Event results in significant symptoms that prevents normal daily activities; may require hospitalization or invasive intervention (e.g., anemia resulting in blood transfusion).

The adverse event information will be reviewed in our monthly team meeting to monitor subject safety. The PI will also monitor the rate of AEs occurring in this study and decide if it is reasonable in light of the rate of AEs in the current literature to continue the study with the medical monitor's input.

The research assistant is responsible to report any AE related to the study to [name] and the PI. The PI will work with the medical monitor to evaluate the event and make a determination of relatedness if the event is related to the study, as it occurs and for notifying the Associate Dean for Research of the UNC School of Nursing and UNC IRB of the occurrence of any adverse event. A scale on relatedness ranging from "Not related to" to "Definitely related to" (Not related to, probably not related to, possibly related to, definitely related to) will be used to evaluate relatedness. Any "definitely related" and "possibly related" events will be reported to the UNC IRB.

The PI will report to the UNC IRB any adverse events that are (1) unexpected, (2) related or possibly related to participation in the research, and (3) serious or suggest that there are new or increased risk(s) to subjects.

**Patient Safety and Confidentiality.** All private health information (PHI) will be kept strictly confidential and subject to the Health Insurance Portability and Accountability Act (HIPAA). All study data in transit will be stored on an encrypted lap top computer stored and locked within the office of the study PI. All transit study data will be back up to the secure SON server that is password protected and maintained by information technology support and then be deleted from the encrypted laptop computer within 72 hours after data are collected. The secure SON server can only be accessed by study personnel on this study. Any new signs or symptoms reported by the patient to the research team will be promptly communicated to the patient's health care team. At the baseline visit, patients will be assessed for any vitamin supplementation, serum creatinine and history of kidney stones. If subjects are currently taking a vit C supplement, we will advise them to stop taking any vitamin C supplement while they are on the study. We also will carefully review with the subjects if they are taking any multivitamin that contains vitamin C and advise them to stop taking any multivitamin that contains vitamin C. Although vitamin C is a water-soluble vitamin, we have implemented these steps to insure safety before randomization.

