### 3. INVESTIGATIONAL PLAN

**Design.** This project is a feasibility pilot study to test the effects of vitamin C supplementation, and to obtain initial estimates of effect size to support a future RCT. The proposed vitamin C supplementation intervention study is a three-group, single blind, placebo controlled prospective design (control n=14, Vit C 500mg n=14, Vit C 1000mg n=14). The most commonly tested dose of vitamin C in current trials on vitamin C supplementation is 1 g/day. The primary endpoint to evaluate the effect of vitamin C supplementation is serum vitamin C level. The secondary outcomes include HF symptom burden, HRQOL, cardiac function, and oxidative stress. The variables would be measured in person at baseline and at 3 months include: HF symptom burden, HRQOL, PROMIS fatigue, depression and sleep disturbance, serum vitamin C level, biomarker of cardiac function (i.e., cardiac output using impedance cardiograph) and oxidative stress (8-iso-PGF2a isoprostane, see below in detail), as well as demographic, clinical, and other variables that can affect study outcomes (e.g., age, gender, race/ethnicity, body mass index, serum creatinine) and medications. HF symptom burden and HRQOL will also be measured at Month 1 and 2 by phone. We will also collect data to assess feasibility (recruitment, retention, attrition rates).

**Sample and Setting.** A total of 42 participants (14 per group) will be randomly assigned to either the control or the intervention group. Patients with HF will be recruited at the University of North Carolina Hospital internal medicine/cardiology outpatient clinics.

**Inclusion/Exclusion Criteria.** Inclusion criteria include patients (a) have a diagnosis of chronic HF. The diagnosis and etiology of chronic HF will be confirmed by a HF cardiologist using established criteria, (b) have undergone evaluation of HF and optimization of medical therapy, (c) are not taking any vitamin C supplementation at all or are willing to stop taking their current vitamin C supplementation, (d) able to read and speak English, (e) have >1 month from any inpatient hospitalization, (e) treating cardiology healthcare provider indicates the individual is a good candidate for this study that involves 3 months of vitamin C supplement of 500 mg/day, 1g/day, or placebo, (f) Per treating healthcare provider's assessment, patient's projected lifespan is greater than or equal to 6 months.

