## 6. CONSENT PROCESS

The consent process includes: 1. Obtain written informed consent from the study subject; 2. Ensure that the most recent version of the IRB-approved consent/HIPAA authorization form is used; 3. Review the informed consent/HIPAA authorization form with the subject in a location that allows privacy; 4. Allow the subject time to read the document and ask questions. Encourage input from family members, if appropriate; 5. Ensure that the subject signs and dates the document in the required sections of the consent and HIPAA authorization form; 6. Ensure the consentor signs and dates (same date) the document in the required section of the consent form; 7. Provide a signed copy of the informed consent/HIPAA form document to the subject; and 8. Document and date consent procedure and file the signed document and checklist back to locked cabinet.

The data (from self-report, impedance cardiograph, and blood drawn) will be collected at baseline clinic appointment and Month 3 in person for all patients. HF symptom burden and HRQOL will be collected at baseline and Month 3, in person and also Month 1 and 2, by phone. All patients will be compensated up to \$50 for participating in this study: \$25 at baseline visit and \$25 at Month 3 visit.

Under special circumstances that we are not allowed to collect in-person data at Month 3 (such as Covid-19 pandemic stay-at-home order that prevents our in-person data collection), we will not collect data from impedance cardiograph or blood drawn. We will only collect self-report data using one of the following 2 ways based on subjects' preference: 1) by phone; 2) by mail-- we will send subjects the questionnaires ahead of time and ask them to complete and send the questionnaire back to us. We also will ask them to send their un-used vitamin C pills back to us by mail.

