The secondary endpoints are symptom burden, HRQOL, cardiac function, and oxidative stress. For Aim 2 to test the effect of a vitamin C supplementation intervention on the secondary endpoint of HF symptom burden from baseline to 3-month follow-up among 3 groups, we will use repeated measure of ANOVA to detect differences in symptom burden from baseline to 3-month follow-up in the intervention group and compared to the control group from baseline to 3-month follow-up. Similarly, to test the effect of a vitamin C supplementation intervention on the secondary endpoint of HRQOL (cardiac function, and oxidative stress) compared to the control group, we will use repeated measure of ANOVA to detect differences in HRQOL (cardiac function, and oxidative stress) from baseline to 3-month follow-up in the intervention group and compared to the control group from baseline to 3-month follow-up.

Similar analysis will be done for adverse events. to test the effect of a vitamin C supplementation intervention on the frequencies of adverse events compared to the control group, we will use ANOVA to compare frequencies of adverse events during the 3-month period among 3 groups.

Sample Size and Power: The total sample size of 42 participants will be selected as a pilot feasibility study. With 42 patients (14 in each group) and an alpha level of .05, the power of the ANOVA F test to detect a significant group difference will be 80% if the effect size is 0.5.

Interim/safety Analysis. We plan to conduct the interim/safety analysis when we have 50% of the intervention sample, and the findings (as well as adverse events) will be reported to the medical monitor. The medical monitor will make decisions about the safety of continuing (or stopping) the protocol, providing recommendations for recruitment, retention, safety, and other issues as appropriate.

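### An adverse event can lead to withdrawal from the study, and nothing keeps withdrawn patients in Month 3 outcome collection, so outcome loss can differ by arm

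*Combined protocol and SAP*

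**What the plan says.** All references are to the combined protocol and SAP.

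- **Section 8 (Safety Evaluations), general rule.** The medical monitor grades each adverse event and is to "advise whether the participant needs to stop taking the investigational pills, withdraw from the study, or any medical treatment is needed". The team follows the advice without delay. Stopping tablets and leaving the study are listed as separate options.
- **Section 8, moderate events.** "we will ask subjects to stop taking their investigational drug, advise them to seek medical treatment, and continue to follow up until the AE resolves".
- **Section 6 (Consent Process).** Self-report, impedance and blood data "will be collected at baseline clinic appointment and Month 3 in person for all patients". The one stated exception is a period when in-person collection is not permitted, and self-report is still collected then.
- **Section 9 (Data Management and Statistical Analysis).** Serum vitamin C and the secondary endpoints are compared from baseline to Month 3 by repeated measures ANOVA. No analysis set and no rule for missing data are given.
- **Section 3 (Investigational Plan).** "A total of 42 participants (14 per group) will be randomly assigned". On loss to the study, the plan says: "We will also collect data to assess feasibility (recruitment, retention, attrition rates").
- **Section 10 (Appendix).** The checklist for high-dose vitamin C names diarrhea, nausea and abdominal bloating.

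**The concern.** The plan recognises two things that can happen after an adverse event, coming off tablets and leaving the study, but does not say what each means for outcome collection. For a patient withdrawn on the monitor's advice, no sentence asks for Month 3 blood, symptom burden or HRQOL. A repeated measures ANOVA on two time points, in its usual form, then omits that patient.

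The route to withdrawal runs through adverse events, and the events the protocol expects are those it attaches to the active product. Loss can therefore be related to arm. The active-arm mean would then describe patients who tolerated their tablets, not everyone assigned to them. Section 3 says the pilot is to supply effect-size estimates for a later trial, and an inflated serum rise would carry forward into that design. Aim 3 is also affected: without separate reporting, intolerance of the tablets appears as attrition from the study.

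**Working it through.** **1. The passages side by side.**

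| Patient after an adverse event | Section 8 | Section 6 | Month 3 outcomes |
|---|---|---|---|
| Mild event, stays on tablets | Event tracked to resolution | All patients measured | Expected |
| Stops tablets only | Event tracked to resolution | All patients measured | Expected, but not said outright |
| Withdrawn from the study on advice | Advice acted on at once | All patients measured, withdrawal not mentioned | Not provided for |

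The gap is firm in the last row. In the second row it is only a lack of explicit wording.

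**2. The plan's own power figure.** Inputs from Section 9: three arms of 14, so N = 42, tested at the 5% level. The claim made there is: "the power of the ANOVA F test to detect a significant group difference will be 80% if the effect size is 0.5". The effect-size metric is not named, so I take it as Cohen's f = 0.5.

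- Noncentrality = N × f² = 42 × 0.25 = 10.5, with 2 and 42 − 3 = 39 degrees of freedom.
- Noncentral F power = 0.803. The stated 80% is reproduced.
- The figure needs all 42 patients measured, because nothing is added for loss. With f held at 0.5 and equal losses across arms, power is 0.769 at N = 39 and 0.729 at N = 36. With assumed losses in the active arms only (14, 12 and 10 measured), it is 0.72 to 0.76 depending on the pattern of means.

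**3. Size of the bias (illustration).** The documents give no withdrawal rate, so k is an assumption. Let k of the 14 in an active arm be withdrawn and unmeasured, let Δ be the mean gain in serum vitamin C among the rest, and suppose those withdrawn would have had no gain.

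- Mean gain over all randomised to the arm = Δ × (14 − k)/14.
- Mean gain among those measured = Δ.
- Ratio = 14/(14 − k).

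| k | Ratio | Overstatement |
|---|---|---|
| 1 | 14/13 = 1.08 | 8% |
| 2 | 14/12 = 1.17 | 17% |
| 3 | 14/11 = 1.27 | 27% |
| 4 | 14/10 = 1.40 | 40% |

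If those withdrawn would instead have kept half the gain, the ratio is 14/(14 − k/2): 14/13 = 1.08 for k = 2 and 14/12.5 = 1.12 for k = 3. If they are measured, the ratio is 1 and this bias is absent.

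**The case against.** The strongest reply is that the plan already covers most of these patients, and for those who only stop tablets that is right. A reader might infer from "continue to follow up until the AE resolves" that a patient taken off tablets for a moderate event is closed once the event ends. The text does not support this. Section 8 ties follow-up to resolution for mild events as well, where tablets continue, so the phrase sets how long the event is tracked and not how long outcomes are collected. Section 6 asks for Month 3 data from all patients. The calls in Section 8 and the Month 3 bottle return in Section 5 apply to all participants, whether or not they still take tablets.

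Other stronger readings also go beyond the documents:

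- That loss would fall mainly in the 1 g arm. No dose-response for intolerance is given, and the checklist is not confined to one arm.
- That the patients lost would have the worst symptom and HRQOL scores. Those scales measure the burden of heart failure, and a digestive event need not mark a poor score. Both are also collected at Months 1 and 2.
- That acceptability of the tablets cannot be told apart from acceptability of the study. Pill counts, calls about daily pill-taking and the checklist would allow it. What is missing is a commitment to report the two separately.
- That the monitor's option to advise withdrawal is itself at fault. The data question can be settled without touching it.

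It is also fair that withdrawal is not automatic at any severity, that its frequency may be low, and that this is a 42-patient feasibility pilot. What remains is that a withdrawn patient has no stated place in Month 3 collection or in the analysis.

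**Conclusion.** The point holds for patients withdrawn from the study after an adverse event. The plan permits the withdrawal, does not provide for their Month 3 outcomes, and uses an analysis that in its usual form leaves them out. For patients who only stop tablets, Section 6 already implies measurement, and an explicit sentence would remove doubt.

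An overstatement of 17% or 27% in an active arm's mean serum rise is an illustration, not an estimate. It assumes 2 or 3 of 14 withdrawn, none measured at Month 3, and no gain in those patients. It carries over in the same proportion to the comparison with placebo only if the placebo arm's mean change is about zero. That loss would be greater in the active arms is an inference from the checklist, not a documented rate. With 14 per arm, a few such patients are enough to matter, and Month 3 blood that was not drawn cannot be recovered later.

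**What to change.** Change data collection and analysis only. The monitor's authority and the rules for stopping tablets stay as they are.

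1. Reconcile Sections 6 and 8. State that a patient who stops tablets keeps the Month 1 and 2 calls and the Month 3 visit, including blood. State that a patient withdrawn after an adverse event is asked for Month 3 outcomes and gives them if he or she agrees.
2. Record the date of the last tablet.
3. In Section 9, state that all patients with data are analysed in their randomised arm, and say how patients still missing at Month 3 are handled.
4. Under Aim 3, report tablet discontinuation and study attrition as separate rates, by arm and with reasons.

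The cost is a few sentences and a few retained visits of a kind planned for every patient. The mean serum rise in the active arms may look slightly smaller, because it would then describe everyone assigned to the dose who could be measured.

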## **1. BACKGROUND:**

### **Heart failure**

Although significant advancements in morbidity and mortality statistics have been established with medical treatment, HF remains a prevalent, morbid, and costly condition. Currently, 6.5 million Americans have heart failure (HF), 50% are readmitted within 6 months of hospital discharge for exacerbations of HF. Thus, hospitals are financially penalized for HF readmissions within 30 days based on the Readmissions Reduction Program initiated by the Centers for Medicare & Medicaid Services. Moreover, patients with HF continue to be symptomatic even after optimization of medical treatment. These symptoms are associated with frequent hospitalization, as well as decreased health related quality of life (HRQOL). Therefore, HF symptom reduction is still the major target of treatment to reduce frequent re-hospitalizations and improve HRQOL.

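### The adverse event definition is built on new symptoms, so no rule has worsening of a symptom already present at baseline graded, reported within 72 hours or counted as a safety event

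*Combined protocol and SAP*

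**What the plan says.** Section 8 (Safety Evaluations) sets the definition: "define as new signs and symptoms after taking investigational drugs", with digestive complaints as the examples. The same sentence adds "any other unanticipated adverse events that could possibly be related to the intervention". Later in that section, the paragraph on patient safety and confidentiality states what goes to the treating clinicians: "Any new signs or symptoms reported by the patient to the research team will be promptly communicated to the patient's health care team". Neither place mentions worsening of an existing symptom, and no other part of the document names worsening heart failure or an exacerbation as an adverse event.

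Section 9 builds the safety comparison on the events so defined: "we will use ANOVA to compare frequencies of adverse events during the 3-month period among 3 groups".

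On the population, section 1 states that "patients with HF continue to be symptomatic even after optimization of medical treatment". On measurement, section 7 describes the heart failure symptom scale (MSAS-HF), which asks whether each symptom was present in the past week: "If present, three characteristics of each symptom will be rated: frequency of symptom, severity of symptom, and degree of symptom distress". Sections 3 and 5 place these ratings at baseline, on the Month 1 and Month 2 phone calls, and at Month 3.

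**The concern.** In a trial of chronic heart failure, much of the deterioration that matters clinically is an existing complaint becoming more frequent, more severe or more distressing. A definition that turns on newness leaves that outside the safety pathway. The same calls that ask about adverse events also collect the ratings that would show a heart failure symptom worsening, yet nothing connects the two.

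Two things are at stake. For the individual patient, marked worsening could be recorded as a questionnaire score without reaching the medical monitor as an event. For the comparison of 500 mg, 1000 mg and placebo, event frequencies could look alike even if one arm had more worsening of existing symptoms. This pilot is meant to inform a later randomised trial, so its safety counts will be carried forward.

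**Working it through.** The point rests on how the provisions fit together. The plan gives no figure for it, and the power statement in section 9 does not enter.

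1. **What depends on the definition.** The 72-hour report to the medical monitor, severity grading, the monthly team review, the relatedness and IRB steps, and the investigator's check of the event rate against the literature (all section 8), and the ANOVA of event frequencies (section 9), apply to adverse events. A change that is not an adverse event enters none of them by rule.

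2. **Test case.** Take a heart failure symptom present at baseline and rated at the bottom of each scale in section 7: frequency 1, severity 1, distress 0. Adding the three ratings, which agrees with the stated maximum of 12, gives 1 + 1 + 0 = 2. At Month 1 the same symptom is rated at the top: 4 + 4 + 4 = 12. The symptom was there before the tablets started, so it fails the newness condition.

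3. **The unanticipated clause.** On the wider reading this is a second, independent limb of the definition. It then requires the event to be unanticipated and possibly related. Section 1 reports that half of patients are readmitted within 6 months of discharge for exacerbations, so worsening is foreseeable in this disease. Whether the clause applies is left to individual judgement.

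4. **The checklist (section 10).** Items 1 to 3 are plain yes/no questions on diarrhea, nausea and bloating, with no newness condition. Item 4 is an open question on unanticipated events or problems. The form can therefore record a pre-existing digestive complaint that the section 8 definition leaves out, while worsening of a heart failure symptom has only item 4. Form and definition do not match.

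5. **The efficacy route (section 9).** Symptom burden and quality of life are compared among the three groups by repeated measures ANOVA, so worsening is compared by arm on average. A mean is a weak detector of individual deterioration: the 10-point rise in step 2 moves that symptom's mean in an arm of 14 by 10/14 = 0.7 points, and a fall of the same size in another patient cancels it. The analysis is described from baseline to 3 months, and use of the Month 1 and Month 2 scores is not stated.

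6. **Link between ratings and safety.** Neither section 5, 7, 8 nor 9 says that a worse rating prompts an adverse event question, a report or a notice to the care team.

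**The case against.** The strongest case against is that worsening does not vanish. Symptom burden and quality of life are secondary endpoints compared among the three groups. The checklist's digestive items ask nothing about newness, and its last item is open. The notice to the care team promises to pass on new complaints but does not forbid passing on others. Patients stay under their own provider, with study visits coordinated with regular clinic visits (section 4). At the interim look, findings as well as adverse events go to the medical monitor. And this is a pilot with 14 per arm; no passage suggests that vitamin C worsens heart failure symptoms.

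Most of this stands as a limit on the point. A reader might infer that worsening is not compared by arm at all, or that none of it can reach the monitor or the care team. The documents do not support either inference: section 9 compares the mean scores, and the checklist, the unanticipated clause, usual care and the interim look are partial routes. A reader might also infer that the symptom scale would show a worsening bowel complaint. Section 7 does not list the eight items, so that cannot be verified.

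What these routes do not supply is a rule. The interim report comes once, at half of the intervention sample, with no stated individual-level criterion. The checklist and the unanticipated clause depend on how the research assistant reads them. A mean efficacy score neither grades nor reports an individual event.

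**Conclusion.** The point holds in limited form. Worsening of a symptom present at baseline is outside the stated adverse event definition and outside the wording of the care-team notice. It is compared by arm only as a mean efficacy score, and no rule has it graded, reported within 72 hours or counted among adverse events. This is a fault in the stated rule, not merely missing detail, because applying the definition as written excludes such cases. It should be corrected, but it does not undermine the trial.

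The number of patients affected cannot be given. It is tempting to convert the 6-month readmission figure in section 1 into a 3-month count. That figure concerns readmission after a recent discharge, whereas this trial requires more than 1 month since any hospitalization and excludes stage D and NYHA class IV. Symptoms can also worsen without readmission, so the figure is neither an estimate nor an upper bound.

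The conclusion assumes that the definition is applied as worded and that worsening heart failure symptoms would usually be regarded as anticipated. If staff routinely treat worsening as an event, the practical gap is smaller, but the text should then say so.

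**What to change.** Make three wording changes:

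- In section 8, define an adverse event as signs and symptoms that are new or have worsened since baseline.
- In the patient safety paragraph of section 8, extend the care-team notice to any new or worsening signs or symptoms.
- In section 10, add worsening of a pre-existing symptom to checklist item 4, so that form and definition agree.

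The symptom ratings already taken at Months 1, 2 and 3 can prompt the checklist question, with the medical monitor judging whether a change amounts to an event. Logging every one-point rise automatically is not advised. Eight items at three time points in 42 patients is up to 8 × 3 × 42 = 1,008 comparisons for one rating alone, and ordinary fluctuation would swamp the event comparison.

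The cost is small: no new data collection, but more, mostly mild, reports for the monitor. The placebo arm shows the background rate. One consequence needs attention. Section 8 ties what happens to the tablets to the grade of the event, so a wider definition brings more events under those rules. The investigators and the medical monitor must reconcile how those rules apply to worsened pre-existing symptoms; no clinical rule is proposed here.
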